Source(s) of Monetary or Material Support	William F. Milton Fund Generative AI Track
Primary Sponsor	Harvard University
Contact for Public Queries	[name] ([contact])
Contact for Scientific Queries	[name] ([contact])
Public Title	Using Conversational AI to Teach Growth Mindset Skills to Youths in India
Scientific title	Using Conversational AI to Teach Growth Mindset Skills to Youths in India: Protocol for a Randomized Controlled Trial
Countries of Recruitment	India
Health Condition(s) or Problem(s) Studied	Youth mental health; anxiety; depression
Intervention(s)	Growth mindset training via 45-minute interaction with conversational AI
Key Inclusion and Exclusion Criteria	
Inclusion Criteria:
 
 - Youth in grades 6-8 at our partner school - Youth assents to participate and a parent/guardian provides passive consent (does not opt-out of participation) 
Exclusion Criteria:
 
 - N/A
Study Type	Interventional
Date of First Enrollment (planned)	Nov 3, 2025
Sample Size	430
Primary outcome(s)	
Change in Behavior and Feelings Survey - Internalizing Subscale (full sample; baseline, 3 weeks, 7 weeks). Trajectories of self-reported symptoms of anxiety and depression from the 6-item (each item rated on a 0-4 scale, with higher ratings indicating more symptoms) Internalizing Subscale of the Behavior and Feelings Survey. Total scores range from 0 to 24, with higher scores indicating more symptoms (BFS; Weisz et al., 2020).
 
Student Perceived Program Acceptability and Helpfulness (intervention group, post-intervention). Assessed via the Program Feedback Scale (Schleider et al., 2019).

Key Secondary outcome(s)	Change in Behavior and Feelings Survey - Internalizing Subscale (elevated subsample ; baseline, 3 weeks, 7 weeks). Trajectories of self-reported symptoms of anxiety and depression from the 6-item (each item rated on a 0-4

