1.1	December 4, 2025	
The questions for growth mindset reflections (intervention group; 3-week, 7-weeks) were reworded for clarity.
 
Old version (1.0):
 
- What do you remember about growth mindset from the session we did a few weeks ago?- Have you used growth mindset for anything at school or home in the past few weeks? If so, please describe how you used it.- How would you most like to use growth mindset in the days ahead? 
New version (1.1):
 
- In one sentence, what is the main idea of growth mindset?- Have you used growth mindset for anything at school or home in the past few weeks?
○ Yes○ Not yet○ I'm not sure- [If they answer “Yes”] Please share what happened. What did you do or think?- How might you use growth mindset in the next month? Be sure to explain:
○ WHAT you want to get better at. This could be a school subject, a skill, or any personal goal.○ HOW you will improve. This could include practicing, asking for help, or any of the tips above!
1.0	November 1, 2025	N/A

3. Roles and responsibilities

3a. Names, affiliations, and roles of protocol contributors

[Refer to page 1 for contributor names and affiliations.]

WT, JSS, SHYT and JRW conceived of the study and developed the initial protocol, with input from SM and JS. WT developed the intervention, with feedback from all other authors. JSS developed the statistical analysis plan, with feedback from WT, SHYT and JRW. Project administration and supervision were provided by WT, JSS and JRW. Funding was acquired by WT, JSS, SHYT, JS and JRW. The original draft was written by WT, JSS and JRW. All authors contributed to the refinement of the final study protocol.

3b. Name and contact information for the trial sponsor

Sponsor:

Office of Research Administration

Faculty of Arts and Sciences

Harvard University

[name]

[name]

[contact]

3c. Role of trial sponsor and funders in design, conduct, analysis, and reporting of trial

The study is funded by the William F. Milton Fund, Generative AI Track at Harvard University. The study is sponsored by Harvard University. The sponsor and funders had no influence over the design, conduct, analysis and reporting of the trial.

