We have extensively tested the chatbot with thousands of AI-generated and human-generated inputs, including malicious ones, to test its safety and appropriateness in a variety of situations. Given such testing, in combination with the already stringent guardrails of OpenAI GPT-4.1, we feel confident that the content of the bot's responses will be appropriate for a school setting. Nonetheless, we will monitor chat logs after each day of the intervention to ensure that all responses from the bot are appropriate. In the unlikely event of inappropriate responses, we will either tighten the guardrails in advance of the next day's session, or we will pause the study until such changes can be made.

15c. Strategies to improve adherence to intervention/comparator protocols, if applicable, and any procedures for monitoring adherence

To help facilitate the study, a researcher will be available over a video call during study-related class periods, and a local assistant will be physically present to help troubleshoot any technical issues. A script is also prepared for the school teacher to read at the beginning of the study (see Appendix D).

15d. Concomitant care that is permitted or prohibited during the trial

N/A

16. Outcomes

Primary Outcomes:

Change in Behavior and Feelings Survey - Internalizing Subscale (full sample; baseline, 3 weeks, 7 weeks). Trajectories of self-reported symptoms of anxiety and depression from the 6-item (each item rated on a 0-4 scale, with higher ratings indicating more symptoms) Internalizing Subscale of the Behavior and Feelings Survey. Total scores range from 0 to 24, with higher scores indicating more symptoms (BFS; Weisz et al., 2020).

Student Perceived Program Acceptability and Helpfulness (intervention group, post-intervention) - Assessed via the Program Feedback Scale (Schleider et al., 2019). This scale consists of 7 items rated on a 1 to 5 scale, with higher scores indicating greater acceptability and helpfulness.

Secondary Outcomes:

Change in Behavior and Feelings Survey - Internalizing Subscale (**elevated subsample**; baseline, 3 weeks, 7 weeks) - Trajectories of self-reported symptoms of anxiety and depression from the 6-item (each item rated on a 0-4 scale, with higher ratings indicating more symptoms) Internalizing Subscale of the Behavior and Feelings Survey. Total scores range from 0 to 24, with higher scores indicating more symptoms (BFS; Weisz et al., 2020).

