Change in Growth Mindset Beliefs (all participants; baseline, 3 weeks, 7 weeks) - Assessed via the Growth Mindset Scale (Sigmundsson & Haga, 2024), adapted to a 6th grade reading level. This scale consists of 8 items, rated on a scale from 1 (not like me at all) to 5 (very much like me).

- In one sentence, what is the main idea of growth mindset?
- Have you used growth mindset for anything at school or home in the past few weeks?
 - o Yes
 - o Not yet
 - o I'm not sure
- [If they answer "Yes"] Please share what happened. What did you do or think?
- How might you use growth mindset in the next month? Be sure to explain:
 - o WHAT you want to get better at. This could be a school subject, a skill, or any personal goal.

- HOW you will improve. This could include practicing, asking for help, or any of the tips above!

Chatbot logs: The logs of all interactions with the chatbot, including timing of messages, will be recorded for analysis.

Potential Moderators:

Demographic questions: age, gender identification, sex assigned at birth, year in school.

Potential Mediator:

Growth Mindset Beliefs: We will conduct a secondary mediation analysis using structural equation modeling (SEM) to test whether change in Growth Mindset mediates the effect of the intervention on change in BFS-Internalizing.

17. Harms

Participants may feel uncomfortable answering some measures of their mental health.

Participants will be told that they have the option to not respond to the questions if they feel uncomfortable or they can rescind their participation in the study. Furthermore, to protect participant responses, we will use a codebook of coded IDs (maintained and owned by the school) so that all IDs collected for research are coded. Given these precautions, we do not anticipate any significant risks associated with this study.

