It is unlikely that participants will become distressed when completing this study and, given that none of the survey questions directly asks about intention to harm oneself or others, such content would not fit into the structure of the intervention or surveys. Nonetheless, if a student should describe mental health distress or an intent to harm themselves or others in the interface to the AI chatbot, the chatbot will respond with empathy and encourage them to call India's national mental health helpline (called TeleMANAS, reachable at [name].). As described in Section 15 (Intervention and Comparator), we have extensively tested the chatbot and are confident that its responses will be appropriate for a school setting. Nonetheless, we will monitor chat logs and in the unlikely event of inappropriate responses, we will either tighten the guardrails or will pause the study.

As our school partner emphasized the importance of respecting the anonymity and confidentiality of student responses as much as possible, we do not plan for researchers or school staff to initiate any outreach to students or parents based on a student's responses to the intervention or surveys.

18. Participant timeline

Each participant engages with the study across five class periods:

- Class 1: Assent and baseline survey
- Class 2 (1 week after class 1): Intervention group receives growth mindset training; control group does typical classroom activities

- Class 3 (1 week after class 2): Intervention group receives growth mindset training; control group does typical classroom activities
- Class 4 (3 weeks after class 3): Follow-up surveys
- Class 5 (4 weeks after class 4): Follow-up surveys; control group receives shortened growth mindset training; intervention group does other classroom activities

Additional detail is provided in the table below, as well as in Appendix A (Study Procedures).

Participant timeline: Schedule of enrollment, interventions, and assessments.

	TRIAL PERIOD					
	Enrollment		Intervention		Follow-Up	
TIMEPOINT	2.5 Weeks Before Enrollment	Enrollment	1 Week After Enrollment	2 Weeks After Enrollment	3 Weeks After Intervention	7 Weeks After Intervention
ENROLLMENT: Parents informed about study & how to opt-out						
	X					
		X				
		X				
		X				
INTERVENTION/ CONTROL: Intervention group receives growth mindset training Control group receives delayed and shortened intervention						
			X	X		
						X
ASSESSMENTS: Demographic questions						
		X				
		X			X	X

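### A low-cost safety improvement, not an error: the helpline message is described only as a chatbot reply, so put it on the closing page of the 7-week survey and in the booklet

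*Combined protocol and SAP*

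**What the plan says.** Section 17 accepts that some mental health measures may be uncomfortable to answer. Its response to that discomfort is "Participants will be told that they have the option to not respond to the questions if they feel uncomfortable", or to withdraw, with coded IDs protecting the answers. It judges distress unlikely and notes that "none of the survey questions directly asks about intention to harm oneself or others".

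The same section then gives its one help route: "if a student should describe mental health distress or an intent to harm themselves or others in the interface to the AI chatbot", the bot answers with empathy and suggests calling the national mental health helpline. Chat logs are reviewed, but the stated purpose is to catch inappropriate replies from the bot. Because the school asked for confidentiality, the plan adds "we do not plan for researchers or school staff to initiate any outreach to students or parents" on the basis of what a student writes or answers. Section 34 plans no ancillary or post-trial care.

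Other safeguards appear elsewhere:
- Section 15c has a researcher on a video call during study periods and "a local assistant will be physically present to help troubleshoot any technical issues".
- Section 32a and Appendix A have the researcher take students' questions at the assent class, with the assistant helping with procedures.
- Section 28a gives the research team general oversight of safety.
- Section 25a says that sessions are supervised and that the school receives a payment for student support.

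On the surveys, Appendix E gives the six BFS items to all participants at 0, 3 and 7 weeks. Section 26 has survey data entered in Qualtrics and chatbot sessions hosted separately. Appendix A (Class 5) places the controls' shortened training after the 7-week survey, and a booklet for every student in grades 6-8 after that class.

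**The concern.** The section names the symptom measures as a source of discomfort, but the helpline message it describes belongs to a different tool. A student unsettled by rating sadness, fear or repeated scary thoughts in Qualtrics would not meet that message there. Controls would not meet it at any of their three symptom surveys, and intervention students would not meet it at baseline. After that, intervention students meet it only if they type distress into the bot.

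What is at stake is participant safety among children in grades 6-8. The plan has already decided that an on-screen pointer to a helpline is a suitable response. The question is only whether that pointer should also appear where the symptom questions are asked.

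**Working it through.** **Step 1. Set the route against the exposure.**

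| Contact with the study | Arm | BFS asked? | Stated helpline route available? |
|---|---|---|---|
| Class 1, baseline | both | yes | no, chatbot not yet used |
| Classes 2-3 | intervention | no | yes, if distress is typed |
| Classes 2-3 | control | no | no |
| Class 4, 3 weeks | both | yes | no, survey only |
| Class 5, 7-week survey | both | yes | no, survey only |
| Class 5, after survey | control | no | yes, if distress is typed |

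Appendix E lists the content of each survey and shows no closing helpline page. None of the other safeguards (skipping items, withdrawing, log review, the people present, team oversight, the payment to the school) is written as a way for a distressed student to reach help.

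**Step 2. Number of students.** Section 19 gives about 450 invited and 5% opting out: 450 × 0.95 = 427.5, which agrees with the plan's figure of about 430. With 1:1 allocation (Section 21b), 430 / 2 = 215 per arm.

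**Step 3. Which surveys remain.** The gaps between classes in Section 18 are 1, 1, 3 and 4 weeks, so the classes fall at weeks 0, 1, 2, 5 and 9. Counting from the planned first enrolment of Nov 3, 2025 (Section 1b):
- Class 4 (3-week survey): Nov 3 + 5 weeks = Dec 8, 2025.
- Class 5 (7-week survey): Nov 3 + 9 weeks = Jan 5, 2026.

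Version 1.1 is dated Dec 4, 2025. That is 4 days before Class 4 and 32 days before Class 5. Baseline has passed.

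**Step 4. Time for approval.** Section 30 dates the initial approval 9/19/2025 and the modification's approval 10/10/2025, a gap of 21 days. This is not a review time, because no submission date is given. Used only as a rough yardstick, Dec 4 + 21 days = Dec 25. That is after Dec 8 and 11 days before Jan 5. On this yardstick the 3-week page is feasible only for classes that enrolled on or after Nov 20 (Dec 25 minus 35 days).

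**Step 5. Reach.** The 7-week page reaches about 430 students, about 215 of them controls. The 3-week survey is not counted, since for classes starting on the planned date approval would probably come too late.

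**The case against.** The strongest objection is that the relevant pages cannot be seen. The parental consent form, assent form and teacher script (Appendices B-D) are not in the available text, and Section 25a says that the data collection forms are available on request. Any of these may already give support contacts. This stands, and it limits the claim to what is shown. It does not remove the point: Appendix E lists the survey content without such a page, so a pointer at the end of the survey would add something even if a form seen weeks earlier gave contacts.

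Second, the plan made a reasoned choice, citing low expected distress, no direct self-harm items and the school's confidentiality condition, and the IRB approved the study. That is why this is an improvement and not an error. None of those reasons argues against a fixed page, which identifies nobody and starts no outreach. Nor does the no-outreach rule stop a student from approaching an adult in the room.

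Third, at the 7-week survey controls are minutes from their own training, so the gap in their arm is nearly over. This is true, but the chatbot gives the helpline only in reply to typed distress, whereas the page gives it to everyone.

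Fourth, version 1.1 is weak evidence that the surveys are easy to edit: "The questions for growth mindset reflections (intervention group; 3-week, 7-weeks) were reworded for clarity" concerns intervention-arm questions only. This is accepted. The low cost rests on the page being static, not on that edit.

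Fifth, a page at the end of the 3-week survey comes before the last BFS rating in an unblinded trial. Any effect is probably small and similar in both arms, but equality is not shown, since some intervention students may already have seen the helpline in the chatbot. This is why the 7-week page and the booklet come first.

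**Conclusion.** The point holds as a low-cost safety improvement. In the visible text, the only stated help route for distress is the chatbot's helpline message, and it does not extend to the surveys where symptoms are rated. The benefit is information for about 430 students at the 7-week survey, about 215 of them controls. This assumes the planned start date, full attendance, an even split and approval before Class 5. If Class 5 has already taken place, no survey remains for the page.

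A reader might infer three stronger things, and the documents support none of them:
- That distressed students are left without help. The unseen forms and screens may give contacts, supervised sessions have adults present, and the team oversees safety.
- That a known number of students are distressed. The plan gives no such figure and none is claimed here.
- That the BFS comparison between arms is biased. Nothing in this point bears on that comparison as planned.

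**What to change.** 1. Put fixed helpline wording on a closing page of the 7-week Qualtrics survey, after the last item (including the intervention arm's reflection questions), identical in both arms and shown whatever the answers. Use set text, since the chatbot's own reply may vary.
2. Print the same wording in the booklet for all grade 6-8 students.
3. Add the page to the 3-week survey only for classes where IRB approval arrives in time, accepting the possible small effect on 7-week ratings.
4. State this in one sentence in Section 17. If the surveys already show the helpline, cite that there instead, and no new survey page is needed.

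The cost is one static page, one line in the booklet, one sentence in the protocol and a small IRB modification. No staff time, outreach or identification of students is required, so the school's confidentiality condition is kept. Sample size, allocation, outcomes and analysis do not change.

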Our growth mindset intervention may also benefit academic performance, and our partner school, at its discretion, may be able to integrate it into part of their standard curriculum following the completion of the study. However, our specific research question is whether the chatbot interaction yields measurable improvements in youth mental health. Given the preponderance of AI chatbots aiming to address various aspects of mental health, such measurement is as important as it is rare. This study will contribute to the growing evidence base on how technology can inform and support youth mental health.

9b. Explanation for choice of comparator

Guided by discussions with the partner school, the control group will undertake alternate classroom activities assigned by the teacher (i.e., treatment as usual) during the intervention periods. The exact activity assigned to the control group will be recorded and reported. The control group will also receive a shortened version of the intervention after 7 weeks. At 7 weeks, all students will receive a printed booklet containing the full content of the intervention.

10. Objectives

The primary objective is to assess the effect of a brief, AI-guided growth mindset training on anxiety and depressive symptoms in youth in India, compared to usual classroom activities, from baseline to 3- and 7-weeks post-intervention. Key secondary objectives include assessing the acceptability of the intervention, assessing the effects on growth mindset beliefs and understanding patterns of engagement with the AI chatbot.

Methods: Patient and public involvement, trial design

11. Patient and public involvement

Inputs from the school partner were vital in developing and refining the intervention content. Critical feedback on the chatbot was provided across three one-hour sessions: (i) by three school teachers, (ii) by two fifth-grade students, and (iii) by a recent 12th grade graduate and a parent of that graduate (all linked to the partner school). These sessions also helped to generate some of the role-playing scenarios that are featured in the chatbot.

12. Trial design

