		X			X	X
				X		
					X	X
Growth mindset reflections (intervention group)						

19. Sample size

Our sample size is constrained by the number of available students in the school. We expect about 450 students to be invited to participate (150/students per grade across 3 grades). Assuming an opt-out rate of 5%, we can expect a sample size of about 430 students.

For our primary tests of intervention effects (i.e., mixed effects model examining the time [baseline, 3-week FU, 7-week FU] * condition [Intervention or Control] interaction), an a priori power analysis shows that our sample size can detect effects as small as 0.22 (using two-tailed tests with $\alpha = .05$, $\beta = 0.2$). This effect size is comparable to that detected by a prior single-session growth mindset intervention (Schleider & Weisz, 2018).

20. Recruitment

All students in grades 6-8 at our partner school will be invited to participate.

The school partner was based on strong pre-existing relationships with the research team. The decision to focus on grades 6-8 was made in consultation with the school principal, who believed that these grades would benefit from the intervention while also having flexibility in their curriculum.

Methods: Assignment of interventions

21. Randomization: Sequence generation

21a. Who will generate the random allocation sequence and the method used

The first author will perform the randomization using R.

21b. Type of randomization (simple or restricted) and details of any factors for stratification.

Simple individual randomization (1:1) of participants to intervention or control group.

22. Allocation concealment mechanism

The use of central randomization will ensure that students and teachers cannot determine trial allocation ahead of time. Allocation to the experimental or control groups will take place when class is not in session (between the day of enrollment and the start of the intervention.)

23. Implementation of randomization

As the study procedures are conducted online, assignment of participants to intervention or control groups is done electronically and not by any personnel. Hence no personnel can influence the implementation of the randomized assignment.

24. Blinding

24a. Who will be blinded after assignment to interventions (e.g., participants, care providers, outcome assessors, data analysts)

The intervention will be unblinded for teachers, students and researchers.

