All statistical analyses will be performed using R. To evaluate intervention effects, we will use a series of mixed-effects regression models implemented via the lme4 package (or comparable tools). Each model will include Time (baseline, 3-week, 7-week), Condition (intervention vs. control), and their interaction (Condition \times Time) as fixed effects, with random intercepts for participants and, where feasible, classroom to account for nesting. The Condition \times Time interaction will test whether outcome trajectories differ between groups over time.

If outcome distributions deviate substantially from normality, we may use generalized linear mixed-effects models with an appropriate link function (e.g., logit, log, or beta) or apply suitable transformations (e.g., rescaling data to a (0,1) interval for beta regression) to improve model fit. All models will be checked for assumptions, including residual distribution and heteroskedasticity.

We will calculate both within-subject and between-subject effect sizes for intervention effects on continuous outcomes. For mixed-effects models, standardized mean differences will be computed from estimated marginal means and pooled residual variance (e.g., using effectsize::t_to_d() or contrasts via emmeans). All effect sizes will include 95% confidence intervals and, when available, Common Language (CL) effect sizes to facilitate interpretation.

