For the mediation analysis, we will use structural equation modeling (SEM) in R (lavaan) to test whether change in Growth Mindset mediates the effect of the intervention on change in BFS-Internalizing. The primary model will specify: Intervention \rightarrow Growth Mindset \rightarrow BFS-Internalizing, with baseline levels of both constructs included as covariates. We will use a latent change score (LCS) mediation model or an observed (composite-score) change model. Indirect effects ($a \times b$) will be estimated using bias-corrected bootstrap 95% confidence intervals, and standardized effects will be reported. Missing data will be addressed using Full Information Maximum Likelihood (FIML) or pooled multiple imputation, consistent with the main analysis. Because indirect effects are typically smaller than direct effects, and given the available sample size ($N \approx 430$), we expect adequate power to detect small-to-moderate indirect effects but limited power for very small ones. Accordingly, this mediation analysis is secondary and exploratory, and findings will be interpreted cautiously.

Transformations

We will examine the distribution of each outcome and apply transformations or generalized linear mixed-effects models as appropriate. For example, if data are heavily right-skewed, we may rescale continuous outcomes to a (0,1) range and fit a **beta-distributed model** to better approximate the observed distribution.

Inference criteria

Two-tailed tests ($\alpha = .05$) will be used.

27b. Definition of who will be included in each analysis and in which group

Participants enter the analysis cohort at randomization, which occurs after assent and baseline measures. Assenting students will be excluded if they do not have the opportunity to complete the baseline measures (e.g., due to interruption or absence) or if they later withdraw consent or assent and ask for their data to be excluded; all others will be included.

All planned analyses will be conducted using the full participant sample (intention-to-treat). We will also conduct subgroup analyses among students with elevated baseline internalizing symptoms—defined as scores ≥ 1 SD above the mean—following established norms for youth mental health measures (e.g., Youth Self-Report; Achenbach & Rescorla, 2001). These analyses will explore whether intervention effects differ when the program is used as a universal versus indicated prevention approach.

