27c. How missing data will be handled in the analysis

We will address missing data using **multiple imputation** via the **mice** package in R. Prior to imputation, we will examine patterns of missingness and conduct sensitivity analyses to assess whether data appear to be **missing at random (MAR)** versus systematically missing. Imputation models will include all variables used in the main analyses and relevant auxiliary variables to support the MAR assumption.

Appropriate imputation methods will be specified by variable type (e.g., predictive mean matching for continuous variables, logistic or polytomous regression for categorical data). For bounded or highly skewed variables, we may apply transformations (e.g., logit or log) prior to imputation and back-transform results after pooling. If multilevel dependencies (e.g., students nested within classrooms) substantially affect missingness patterns, we will use multilevel imputation approaches (e.g., miceadds or mitml) to preserve the nested data structure.

The number of imputed datasets will approximately match the percentage of missing data for each outcome (rounded up to the nearest whole number, e.g., three imputations for $\sim 2\text{--}3\%$ missingness). Analyses will be pooled across imputations using **Rubin's rules**, providing **intent-to-treat** estimates that retain power and reduce bias relative to listwise deletion.

Effect sizes (e.g., Cohen's d with 95% confidence intervals) will be derived from model-based estimates using the **effectsize** or **MOTE** packages in R, based on t -values from treatment effects in the pooled analyses.

27d. Methods for any additional analyses (e.g., subgroup and sensitivity analyses)

1) We will conduct exploratory qualitative analyses of participants' growth mindset reflections using AI-based text analysis tools, supplemented by manual review where appropriate. In addition to categorizing responses into themes, we will code whether reflections demonstrate (a) valid understandings of growth mindset, (b) positive applications of growth mindset in real-life contexts, or (c) specific intentions to apply growth mindset principles. We will also explore whether baseline demographic variables are associated with the presence or absence of these codes.

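### The primary mixed model estimates a baseline gap between arms that randomization makes zero, which costs precision; random intercepts alone can also mis-state the SE of single follow-up contrasts

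*Combined protocol and SAP*

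**What the plan says.** Section 27a sets out the primary model: "Each model will include Time (baseline, 3-week, 7-week), Condition (intervention vs. control), and their interaction" enter "as fixed effects, with random intercepts for participants and, where feasible, classroom to account for nesting". Baseline is therefore an outcome occasion, and the Condition main effect leaves the baseline difference between arms as a free parameter. The interaction is the test of effect. The plan does not say whether that means the joint 2-df test, one follow-up contrast or a linear slope.

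Section 27b fixes the order of events: "Participants enter the analysis cohort at randomization, which occurs after assent and baseline measures".

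Baseline adjustment appears only in the mediation model of Section 27a, which is fitted "with baseline levels of both constructs included as covariates". Section 27c derives effect sizes and their 95% confidence intervals "based on t -values from treatment effects in the pooled analyses". Section 10 states the objective as an effect "compared to usual classroom activities, from baseline to 3- and 7-weeks post-intervention". Section 19 explains that N cannot grow: "Our sample size is constrained by the number of available students in the school".

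**The concern.** There are two separate issues.

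**Precision.** When baseline precedes randomization, any observed baseline gap is chance. A model that estimates the gap freely subtracts it in full from each follow-up difference and so carries its noise into the treatment effect. A model that gives both arms one baseline mean, or conditions on baseline, removes only the part that baseline predicts. It is never less precise for a single follow-up contrast. Enrolment is capped, so the analysis is the only remaining source of precision.

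**Standard errors.** Random intercepts alone imply one common correlation between every pair of waves. The waves are unequally spaced, and nearer waves often correlate more strongly. If they do here, the model averages the correlations. It then understates the SE of the baseline-to-7-week contrast and, under more than mild fading, overstates that of the 3-week contrast. A t-value belongs to a single coefficient, so this reaches the reported confidence intervals even if the 2-df test is the primary one.

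**Working it through.** **Inputs.** From Section 19: N of about 430, taken as 215 per arm; two-sided α of 0.05; 80% power; detectable effect 0.22, with no standardizer stated. From Section 18 ("Class 4 (3 weeks after class 3): Follow-up surveys", and class 5 four weeks later): baseline to 3-week survey is 1+1+3 = 5 weeks, 3-week to 7-week survey is 4 weeks, baseline to 7-week survey is 9 weeks. Assumed because the documents are silent: the correlation ρ between waves, equal variances (SD = 1), complete data, and 0.22 in raw SD units.

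**1. The plan's own figure.** N reproduces: 450 × 0.95 = 427.5. The 0.22 cannot be reproduced, because no correlation, standardizer or contrast is given. It is attainable. With a free baseline, 80% power for a single follow-up contrast needs

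ρ = 1 − (0.22/2.8016)² × 215/4 = 0.67.

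With baseline constrained it needs

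ρ = √[1 − (0.22/2.8016)² × 215/2] = 0.58.

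**2. Variance of one follow-up contrast.**

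- Planned: 2(1−ρ) × 2/215
- Constrained or adjusted: (1−ρ²) × 2/215
- Ratio, constrained to planned: (1+ρ)/2, so the information given up is (1−ρ)/2

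With unequal variances, the difference between the two is proportional to (σ₀ − ρσₜ)², which is never negative.

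**3. Single-contrast power at 0.22**, Φ(0.22/SE − 1.96). At ρ = 0.5 the planned SE is √(1.00 × 2/215) = 0.0964 and the constrained SE is √(0.75 × 2/215) = 0.0835.

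| ρ (assumed) | Information given up | Power, planned | Power, constrained |
|---|---|---|---|
| 0.3 | 35% | 0.49 | 0.67 |
| 0.5 | 25% | 0.63 | 0.75 |
| 0.6 | 20% | 0.72 | 0.81 |
| 0.7 | 15% | 0.84 | 0.89 |
| 0.9 | 5% | 0.999 | 0.999 |

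**4. The 2-df interaction test.** With 0.22 at both follow-ups, the noncentrality is 215 × 0.22²/[3(1−ρ)] as planned and 215 × 0.22²/[(1−ρ)(1+2ρ)] constrained. At ρ = 0.5 these are 6.94 and 10.41.

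| ρ (assumed) | Planned | Constrained, effect at both follow-ups | Constrained, effect at 7 weeks only |
|---|---|---|---|
| 0.5 | 0.65 | 0.83 | 0.71 |
| 0.6 | 0.75 | 0.88 | 0.79 |
| 0.7 | 0.87 | 0.94 | 0.89 |

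The planned power is the same whether the effect is at both follow-ups or at 7 weeks only.

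**5. Type I error under random intercepts alone.** The model uses 2(1−ρ̄), where ρ̄ is the mean of the three correlations; the true contrast variance uses that contrast's own ρ. The actual error is 2[1 − Φ(1.96 × √((1−ρ̄)/(1−ρ₀ₜ)))]. For the moderate pattern at 7 weeks, ρ̄ = 0.633 and √(0.367/0.45) = 0.903, which gives 7.7%.

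| Correlations 0–3 / 3–7 / 0–7 wk (assumed) | 7-week contrast | 3-week contrast |
|---|---|---|
| Equal | 5.0% | 5.0% |
| Mild decay: 0.65 / 0.68 / 0.62 | 6.0% | 5.0% |
| Moderate decay: 0.65 / 0.70 / 0.55 | 7.7% | 4.5% |
| Exponential decay: 0.65 / 0.71 / 0.46 | 9.4% | 3.8% |

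Coverage of the 7-week 95% interval is correspondingly 95%, 94%, 92.3% and 90.6%. Simulation (20,000 trials per pattern, simple randomization, N = 430) agrees with the analytic values to within about half a percentage point. The 2-df test stays between 5.0% and 5.5%. If Time were coded as a linear slope, the error would be 5.9–6.1%, 7.5–7.8% and 9.2–9.5% under the three decay patterns.

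**The case against.** The planned model is a standard, valid analysis of change from baseline, which is what the objective asks for. The loss is one of efficiency only. That stands, and no bias is alleged.

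The low-ρ rows also fit poorly with the plan's own power claim. If 0.22 is in raw SD units and 80% power is right, ρ must be about 0.67 for a single contrast or 0.64 for the 2-df test. At those values the gain is smaller: 0.80 to 0.87 for the single contrast; for the 2-df test, 0.80 to 0.90 with the effect at both follow-ups and 0.80 to 0.83 with it at 7 weeks only. This is a fair anchor, but ρ is not stated, so the range has to be shown. The gain remains at the anchor.

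On standard errors, three labelled occasions most naturally mean categorical Time and a 2-df test, which is barely affected. Exponential decay with no stable student component is an extreme pattern. Both points stand. The issue is then confined to single contrasts and the intervals built on them, which the plan does intend to report.

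The plan allows tools comparable to lme4, and its list of model checks is not exhaustive. It nevertheless commits to no covariance check and no baseline constraint.

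Finally, changing a registered primary model has a credibility cost. That is a reason to date and log the change before outcomes are analysed.

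**Conclusion.** The concern holds and should be acted on; it is not a validity failure. The free baseline gap gives up (1−ρ)/2 of the information in each follow-up contrast: 15% to 25% for ρ between 0.7 and 0.5, and little at 0.9. The direction of the loss follows from algebra; its size rests on the assumed ρ, and the power figures also assume raw SD units, 215 per arm, equal correlation and complete data. The gain applies to both the 2-df test and a single contrast.

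The error-rate issue is conditional. It arises only if correlation fades with time and a single 7-week contrast, its interval or a linear slope is used for inference. In that case the 7-week error rate is about 6% under mild decay and up to 9.4% under exponential decay.

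**What to change.** Before outcomes are analysed:

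- State that Time is categorical, and name the primary test: the 2-df interaction or one given follow-up contrast.
- Give both arms one baseline mean (Time plus Condition-by-follow-up terms, no Condition effect at baseline). Alternatively, model the 3- and 7-week scores with baseline BFS and its interaction with time as covariates. The two agree only if that interaction is included and data are complete.
- Use an unstructured within-student covariance, for example mmrm or nlme::gls with class as a fixed factor. To keep the planned classroom random intercept, stay in lme4 and add cluster-robust SEs by student.
- Carry the baseline and baseline-by-time covariates into the beta or generalized fallback model, if it is used.
- Do the same for Growth Mindset.

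No new data are needed. The cost is procedural: this changes a pre-registered primary model after the planned first enrolment (3 November 2025, Section 1b), with researchers unblinded (Section 24a). It must be dated and logged in the protocol and registry, with IRB approval under Section 31 if deemed substantive. An unstructured covariance needs a package other than lme4, which Section 27a already permits. Reporting the registered model alongside as a sensitivity analysis would keep the change transparent.
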